10.7.4 Evaluation of Assistive MIBG Scoring System

The performance characteristics of the assistive MIBG scoring system will be described, using NANT nuclear medicine central review as the gold standard. Scatterplots and a general measure of

concordance (the concordance correlation coefficient ¹¹⁶ or the weighted kappa statistic ¹¹⁷, depending on the distributions of the nuclear medicine central review scores, will be used to summarize the agreement of the two measures. Since the long-range goal would be to replace standard nuclear medicine Curie scoring with the assistive scoring, regression methods will also be used to evaluate how well the assistive score can “predict” the gold standard score.

10.7.5 Evaluation of NET Expression and Clinical Response to ¹³¹I-MIBG

NET immunohistochemistry results will be coded on a semi-quantitative intensity scale (0 – 3). We will utilize Fisher’s exact test to compare categories of NET intensity between patients with and without response to the first course of therapy (according to 10.3.1).

In a secondary analysis, we will also attempt to validate a previous report of lower NET expression among patients with *MYCN* amplified tumors. We will perform Fisher exact test to compare categories of NET expression between patients with *MYCN* amplified vs. non-amplified tumors.

10.7.6 Concordance of Institutional and Central Assignment of Curie Score

Treating institutions and NANT MIBG scan central reviewers will each assign patients a Curie score at diagnosis, end of course 1, and end of course 2 (if applicable). For the purposes of this exploratory aim (aim 1.9), the analytic cohort will include any of these scans assigned a Curie score by an institution that does not include a designated NANT MIBG scan central reviewer. Descriptive statistics will be provided that include 1) concordance rate between institutional and central review as well as 2) the percent of patients for whom MIBG response category (per section 11.3) would change based upon differences in Curie score between institutional and central review. Analysis of the Curie scores will be the same as described in 10.7.4, with the gold standard being the NANT MIBG scan central reviewer. For the comparisons of overall response, data will be summarized with contingency tables and the weighted kappa statistic.

10.7.7 Sinusoidal Obstruction Syndrome after ¹³¹I-MIBG Therapy

For the purposes of assessing Aim 1.10, the number of patients treated with protocol therapy who go on to receive subsequent myeloablative therapy with stem cell rescue within 6 months of completing study therapy will be determined based upon data collected during protocol follow-up. Of this population, the number and percent of patients who develop SOS of any grade within 21 days of stem cell rescue after myeloablative therapy will be reported based upon specific query on protocol follow-up forms.

For the purposes of this protocol, the definition of SOS will mirror the definition used in NANT and COG trials that include myeloablative therapy: serum total bilirubin > 2.0 mg/dL, with at least 2 of the following findings within 21 days of receipt of stem cell infusion after myeloablative therapy:

- hepatomegaly with right upper quadrant pain;
- ascites; or
- weight gain >5% above baseline.

Severe SOS is defined as an episode of SOS in addition to a specific organ failure:

- a. Hepatic encephalopathy (CTC Grade 4 hepatic failure), OR
- b. Pulmonary dysfunction: Continuous oxygen support (CTC Grade 3 hypoxia) for > 48 hours, ventilatory support not clearly attributable to another cause, OR
- c. Renal dysfunction: serum creatinine > 3 times the ULN (CTC Grade 3 creatinine), or the need for dialysis (CTC Grade 4 renal), not clearly attributable to another cause.

All other cases of SOS not meeting the definition of severe SOS will be considered mild-moderate.

Additional details, including time from last ¹³¹I-MIBG to start of myeloablative therapy, type of conditioning for myeloablative therapy, severity of SOS, need for defibrotide therapy, and outcome of SOS will be collected and reported descriptively. The number of patients undergoing myeloablative therapy and the number of those patients developing SOS will be reported according to randomized arm assignment.

10.7.8 Circulating Tumor DNA (ctDNA)

Evaluation of ctDNA in the context of this trial is considered a pilot investigation. Descriptive data on percent of patients with detectable ctDNA at each time point will be reported for the entire cohort and then separately for responders and non-responders (as defined in section 10.3). Data using next generation

sequencing method and ddPCR method obtained from the same time point will be presented using descriptive statistics, with no formal statistical testing planned.

10.8 Inclusion of Women and Minorities

The study is open to all participants regardless of gender or ethnicity. Review of accrual to past NANT studies of new agents demonstrates the accrual of both genders and all NIH-identified ethnicities to such studies. Although we will summarize the response rate by gender and race/ethnicity, the relatively small number of patients entered into this trial will not permit formal comparisons.

11.0 NANT RESPONSE CRITERIA v 1.2

Below are the NANT Response Criteria. Since patients on this study must have MIBG avid tumors, any reference to MIBG non-avid tumors is not applicable.

Overall response will incorporate all three parameters: CT/MRI, MIBG (FDG-PET is substituted for MIBG non-avid tumors), and bone marrow response with overall response defined as outlined in Section 11.6. Response for each parameter and overall response will be reported by the treating site using the criteria below. However, the final statistical analysis of response will utilize responses as graded by central review, using the same criteria below.

11.1 Response Criteria for CT/MRI Lesions

For lesions evaluated by CT/MRI, this study will use the definitions of measurable disease from the Response Evaluation Criteria in Solid Tumors (RECIST 1.1; European Journal Cancer 45: 228-247, 2009) modified per the criteria below to define target lesions (lesions which are measurable AND evaluable for response).

11.1.1 Definition of soft tissue TARGET LESIONS on CT/MRI:

Soft tissue target lesions that will be followed for response must meet criteria in a. and b. below:

- a. A target lesion must be measurable, defined as a soft tissue lesion that can be accurately measured in at least one dimension with a longest diameter ≥ 10 mm, or for lymph nodes ≥ 15 mm in short axis. (The short axis is measured after identifying the longest diameter of a lymph node or nodal mass, and then measuring the longest perpendicular diameter to that as the short axis).
- b. A target lesion must also be evaluable for response: To be evaluable, the lesion must also be MIBG or FDG-PET avid (if tumor known to be MIBG non-avid), or have a biopsy as required in the eligibility criteria. If one soft tissue lesion present at enrollment is biopsied showing neuroblastoma or ganglioneuroblastoma at any time point, then all other soft tissue lesions present at enrollment are considered evaluable. Bone marrow positivity does not affect soft tissue evaluability.

NOTE: Soft tissue components of bone lesions will be considered measurable lesions if > 10 mm in at least one dimension, and evaluable for response if MIBG avid (or PET-avid if tumor known to be MIBG non-avid).

Serial measurements of target lesions are to be done with the same method of assessment (either CT or MRI) used to characterize each lesion reported at baseline. The sum of diameters (longest for non-nodal lesions, short axis for nodal lesions) for all target lesions will be calculated and reported as the **sum of diameters**.

11.1.2 Non-Target soft tissue lesions will include:

- a. Leptomeningeal tumor and tumor in cerebrospinal fluid cytology will be considered non-target lesions.
- b. Lesions that are considered likely to be active tumor by the treating physician based on clinical correlation (for example, hepatic and pulmonary nodules)

11.1.3 The following lesions will NOT be followed to evaluate response either as target lesions or non-target lesions, if they meet the criteria below **AND** the treating physician feels they are unlikely to represent active tumor (an exception for active tumor will be made for c. below):

- a. Measurable soft tissue lesions (≥ 10 mm) that are not MIBG avid or PET avid (if tumor known to be MIBG non-avid) and if biopsied did not show neuroblastoma or ganglioneuroblastoma.
- b. Non-measurable soft tissue lesions < 10 mm or non-measurable lymph nodes (defined as lymph nodes > 10 to < 15 mm on short axis).
- c. Intramedullary bone lesions will not be followed for CT/MRI response even though they are felt to represent active tumor since they will be evaluated with MIBG scans (or FDG-PET scans if MIBG non-avid), and since bone changes on CT/MRI are known to persist after resolution of active tumor.

11.1.4 The response of the CT/MRI lesions will be defined as outlined below:

11.14.1 Complete Response (CR)

Disappearance of all target CT/MRI lesions.

11.1.4.2 Partial Response (PR)

At least a 30% decrease in sum of diameters of CT/MRI lesions, (using longest diameter for non-nodal lesions and short axis for nodal lesions), taking as reference the measurement of target lesions performed at study enrollment. Non-target CT/MRI lesions must be stable to smaller in size. No new lesions. MIBG (PET-FDG for MIBG non-avid tumors) uptake may still be present in lesions positive at enrollment.

11.1.4.3 Progressive Disease (PD)

At least a 20% increase in sum of diameters of target lesions (using longest diameter for non-nodal lesions and short axis for nodal lesions), taking as reference the smallest sum of diameters while on study (this includes the baseline if that is the smallest on study). In addition to the relative increase of 20%, the sum must also demonstrate an absolute increase of 5 mm. A new target or non-target tumor lesion seen on CT/MRI without MIBG or PET uptake is considered PD, but may be biopsied to rule out PD. An overall substantial worsening of non-target CT/MRI lesions is also considered as a criteria for PD (guidance for substantial includes a 73% increase in volume, of sufficient worsening of overall non-target disease such that the treating physician feels a change in therapy is indicated).

New uptake of MIBG (or FDG-PET for MIBG non-avid tumors) at target and/or non-target lesions which are stable in size, will be captured in MIBG response (or FDG-PET if tumor is MIBG non-avid) and will NOT be graded as CT/MRI progression. CT/MRI would be graded as SD. Biopsy of such lesions can be done to rule out PD for the MIBG (or FDG-PET) response.

11.1.4.4 Stable disease (SD)

(Applies only to patients with target lesions)

Neither sufficient shrinkage in sum of diameters to qualify for PR, and patient does not meet any criteria for PD. No new lesions. Non-target lesions must be stable to smaller in size.

11.1.4.5 Stable disease-no target lesions (SD-NTL)

(Applies to patients with non-target lesions only)

Non-target lesions are still present; may be smaller or stable in size, and do not meet criteria for PD. No new non-target tumor lesions (new lesions may be biopsied to rule out PD).

11.1.4.6 Not involved (NI)

No target or non-target lesions

11.1.4.7 Non-target lesions only

Patient has no target lesions, but does have non-target lesions

11.1.4.8 Not evaluable (NE)

CT/MRI scans are of inadequate quality as assessed by central reviewer, or scans are not repeated of all lesions with tumor documented at entry. (Note that patients not evaluable at a given time point may be evaluable for response at later time points if all scans done with adequate quality at later time point.) Or if based on Study Management Committee/PI review it is deemed that there is insufficient data to grade response

11.1.4.9 Not done (ND)

No CT/MRI scans were done at the given time point.

11.2 Response Criteria for Morphologic Bone Marrow Disease

Routine morphology (with or without routine immunocytochemistry) will be used for baseline evaluation and all subsequent response evaluations performed while on protocol therapy, and at end of protocol therapy. Central review will be performed on bilateral biopsies only unless tumor is seen only on aspirates.

Patients with $\leq 5\%$ tumor on all samples of the bilateral bone marrow aspirate and biopsies at study entry will be evaluable for bone marrow response, but defined separately from patients with $>5\%$ at study entry.

The percentage of tumor in an aspirate will be calculated as the number of tumor cells divided by the number of total nucleated cells. The percentage of tumor in a biopsy will be calculated as the percent of tumor cells (including neuroblasts, mature and maturing ganglion cells) based on the bone marrow parenchymal surface area examined (excluding Schwannian stroma).

11.2.1 Complete Response (CR)

Greater than 5% tumor cells seen on any one sample of bilateral aspirates/biopsies performed at study entry, with no tumor cells seen on bilateral aspirates and biopsies at one subsequent time point.

11.2.2 Complete Response-Minimal Residual Disease (CR-MRD)

Percentage tumor $\leq 5\%$ on all samples of bilateral aspirates/biopsies at study entry, with no tumor cells seen on bilateral aspirates and biopsies at one subsequent time point after starting protocol therapy. If subsequent time points remain negative, then patient is classified as CR-MRD. If subsequent time points are intermittently positive but with $\leq 10\%$ tumor, then response should be reclassified as SD at the negative time points initially reported as CR-MRD.

11.2.3 Progressive Disease (PD)

Patients with any amount of tumor in the bone marrow at study entry will be considered to have PD if one subsequent evaluation shows $> 10\%$ tumor on any one bone marrow sample AND there is a doubling in the amount of tumor compared to study entry (baseline).

For example, a patient entering with $\leq 5\%$ tumor in marrow must increase to $\geq 10\%$ tumor to have PD; a patient entering with 30% tumor must increase to $\geq 60\%$ tumor. If patients have an increase in tumor amount which is less than the amount specified for PD, the response will be classified as SD.

Patients who enter on study with no tumor seen will be considered PD if ONE subsequent evaluation shows $>10\%$ tumor. If $\leq 10\%$ tumor is seen on one subsequent evaluation or intermittently, the response will be classified as SD.

11.2.4 Stable Disease (SD)

Stable disease will be defined as persistence of an amount of tumor in the bone marrow that does not meet criteria for progressive disease or CR or CR Minimal Residual Disease. (Note that patients who enter with any amount of tumor and have one subsequent negative bone marrow which is initially graded as a CR or CR-MRD and then on subsequent time points have 1-10% tumor noted would be then considered as SD at all time points, including the time point initially graded as CR/CR-MRD).

11.2.5 Not Evaluable (NE)

Patients for whom follow-up bone marrows do not include an attempt to obtain bilateral aspirates and biopsies and do not have at least one adequate biopsy sample, as assessed by local site's pathology report for that time point or if based on Study Management Committee/PI review it is deemed that there is insufficient data to grade response.

11.2.6 Not involved (NI)

Patients with no evidence of neuroblastoma in the bone marrow at study entry, and remain negative on subsequent evaluations. (Note that such patients may be reclassified as SD if they meet the SD criteria above with intermittent tumor in the bone marrow).

11.2.7 Not done (ND)

Bone marrow evaluation not done at a given time point.

[figure not shown]
11.3. **Response Criteria for MIBG Avid Lesions**

MIBG Response will be graded using the Curie scoring scale.¹⁰⁶ The treating site will report the MIBG response using the Curie scoring, however the statistical endpoint of MIBG response will utilize the Curie score from the central reviewer.

MIBG scans will be scored for 10 regions: 9 anatomic regions for skeletal metastases, and a 10th region for any MIBG avid soft tissue disease.

Each of the 10 regions will be given a score of 0-3, as defined below.

Scoring of Skeletal Disease Regions 1 – 9	
Scoring	MIBG uptake
0	No MIBG uptake
1	1 focal lesion
2	> 1 focal lesion
3	> 50% of a region

The **absolute extension score** is obtained by adding the scores of all ten regions. The presence of an MIBG avid lesion, and NOT the “intensity” of MIBG-avidity, determines the scoring within a particular region.

REGIONS 1-9 (SKELETAL DISEASE): Cranio-facial disease is scored in Region 1, cervico-thoracic spine in Region 2, ribs/sternum/clavicles/scapula in Region 3, lumbar-sacral spine in Region 4, pelvis in Region 5, humeri in Region 6, distal upper extremities in Region 7, femurs in Region 8, and distal lower extremities in Region 9 (see figure below).

Region 10 (SOFT TISSUE DISEASE): Soft tissue disease within the neck, chest or abdomen/pelvis is scored within Region 10. Examples of soft tissue lesions may include MIBG avid cervical, paraspinous, adrenal, renal, retroperitoneal, or hepatic masses.

SCORING SOFT TISSUE DISEASE: Score = 1 indicates an isolated soft tissue mass that encompasses < 50% of that region (chest or abdomen/pelvis). Score = 2 indicates > 1 soft tissue lesion in the neck, chest or abdomen/pelvis. A soft tissue score = 3 indicates MIBG avid soft tissue disease that encompasses > 50% of either the chest or abdomen/pelvis. (For example, a large adrenal mass in which the MIBG avidity encompasses > 50% of the abdomen/pelvis is scored a 3 for Region 10). Cervical soft tissue disease is included in the chest region.

If no MIBG-avid soft tissue lesions are present, then score 0 for Region 10.

If a solitary soft tissue lesion extends into both the chest and abdomen/pelvic regions, score 3 for that lesion. For example, a large paraspinal mass that extends along the thoracic and lumbar spine would be scored a 3 for Region 10. Any corresponding metastatic bone disease within the thoracic or lumbar spine would be scored separately for the cervico-thoracic spine (Region 2) and lumbar spine (Region 4).

Conjugate planar imaging will be used to score a given region. SPECT scans may be used as an adjunct, but only to help delineate the location of the MIBG avid lesion.

The **relative score** is calculated by dividing the absolute score at each time by the corresponding pre-treatment overall score. The relative score of each patient is calculated at each response assessment and classified as below:

- a. Complete response: all lesions of uptake on MIBG scan completely resolved.
- b. Partial response: Relative score ≥ 0.1 to ≤ 0.5
- c. Stable disease: Relative score > 0.5 to < 1.2
- d. Progressive disease: New lesions on MIBG scan OR a relative score ≥ 1.2 . Biopsy of new lesions may be done to rule out progressive disease. If biopsy is negative for tumor (neuroblastoma and/or ganglioneuroblastoma), patient will not meet definition of PD.
- e. Not evaluable: MIBG scan of inadequate quality as assessed by central reviewer.
- f. Not involved: No MIBG avid lesions at study entry and subsequent response time points.
- g. Not done: MIBG scan not done at a given response time point.

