11.6.1 Complete Response (CR)

Response of CR or NI for MIBG (FDG-PET if tumor is not MIBG avid), CT/MRI and bone marrow.

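### Section 11.3 assigns no MIBG grade to a relative Curie score above 0 and below 0.1, so on the literal text a near-complete MIBG response cannot count toward the primary endpoint

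*Combined protocol and SAP*

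**What the plan says.** Section 11.3 builds an absolute score from ten regions: "Each of the 10 regions will be given a score of 0-3, as defined below". The relative score is the score at an assessment divided by the pre-treatment score, and each patient's relative score is then to be placed in one of the listed classes:

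- CR: "Complete response: all lesions of uptake on MIBG scan completely resolved".
- PR: "Partial response: Relative score ≥ 0.1 to ≤ 0.5".
- SD: "Stable disease: Relative score > 0.5 to < 1.2".
- PD: a new lesion, or a relative score of 1.2 or more. New lesions may be biopsied: "If biopsy is negative for tumor (neuroblastoma and/or ganglioneuroblastoma), patient will not meet definition of PD".
- "Not evaluable: MIBG scan of inadequate quality as assessed by central reviewer".
- Not involved and not done: no avid lesions at entry or later, and no scan at that time point.

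For analysis, "the statistical endpoint of MIBG response will utilize the Curie score from the central reviewer". Overall CR under 11.6.1 is "Response of CR or NI for MIBG (FDG-PET if tumor is not MIBG avid), CT/MRI and bone marrow". Overall CR-MRD (11.6.2) also needs MIBG CR or NI. Overall PR (11.6.3 and the table in 11.6.10) needs MIBG PR, CR or NI, together with qualifying CT/MRI and marrow grades. Section 10.3.1 counts only CR, CR-MRD and PR as response, and Section 10.1 selects the arm with the best observed response rate after one course.

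**The concern.** The list in 11.3 is meant to classify every score, but it leaves an interval empty between CR and PR. The result is not monotone: a larger fall in Curie score can lose the grade that a smaller fall earns. The patients concerned have the best MIBG results short of complete resolution.

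The gap reaches the primary endpoint because Section 3.2.5 requires MIBG uptake at entry. NI is therefore not available as an MIBG grade, and overall response always depends on grading the MIBG scan. At stake is whether a patient with a fall of more than 90% is counted as a responder in a trial that selects a regimen on the observed response rate.

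**Working it through.** The plan states no figure to reproduce here. The check applies the 11.3 rules literally to every attainable pair of scores.

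**Inputs** (all from 11.3): ten regions at 0 to 3 points, so the score runs from 0 to 10 × 3 = 30; relative score r = f/b, with baseline b from 1 to 30 and follow-up f from 0 to 30; the cut-offs quoted above. Scans are taken as adequate and new lesions as absent.

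**Example, baseline 20:**

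| Follow-up | r | MIBG grade |
|---|---|---|
| 0 | 0 | CR |
| 1 | 1/20 = 0.05 | none |
| 2 | 2/20 = 0.10 | PR |
| 10 | 10/20 = 0.50 | PR |
| 11 | 11/20 = 0.55 | SD |

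**Where the gap lies.** No grade applies when 0 < f/b < 0.1, that is f ≥ 1 and b > 10f.

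- f = 1: b = 11 to 30, 20 pairs.
- f = 2: b = 21 to 30, 10 pairs.
- f = 3: b would have to exceed 30, so none (3/30 = 0.10 is PR).
- Total: 20 + 10 = 30 pairs.

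The ratios run from 1/30 = 0.033 to 2/21 = 0.095, which are falls of 96.7% and 90.5%.

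**Regions needed at baseline.** With at most 3 points per region, b = 11 needs 11/3, rounded up to 4 regions. b = 21 needs 21/3 = 7.

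**All 30 × 31 = 930 pairs.** As written: CR 30, PR 195, SD 300, PD 375, no grade 30. With the lower bound of PR changed to > 0: CR 30, PR 195 + 30 = 225, SD 300, PD 375, no grade 0. No other pair changes grade.

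**Rounding.** No precision is stated. If r were rounded half up to one decimal (an assumption), residual 1 with baseline 11 to 20 becomes 0.1 (1/20 = 0.05 rounds up), as does every residual-2 pair (smallest 2/30 = 0.067). That moves 10 + 10 = 20 pairs to PR. Residual 1 with baseline 21 to 30 (0.048 down to 0.033) rounds to 0.0. Uptake has not resolved, so this is not CR, and 0.0 is below 0.1, so it is not PR. Ten pairs still have no grade.

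**From MIBG grade to overall response.** Take an ungraded MIBG result with CT/MRI of CR, PR, NI or SD-NTL, and marrow of CR, CR-MRD, NI, or SD with at most 5% tumor. With MIBG PR these combinations can give overall PR under 11.6.3. With no MIBG grade, none of 11.6.1 to 11.6.3 is met, so 10.3.1 leaves the patient among the non-responders.

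**Weight of one patient.** 1/35 = 2.9 percentage points on a full arm.

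**The case against.** The strongest reply is that nobody would apply the text this way. Section 10.3.1 requires every registered patient to be placed in a response category, so a reviewer facing a fall from 20 to 1 must choose, and PR is the only choice that respects the order of the grades. The CT/MRI definition of PR (11.1.4.2) has no floor of this kind, and neither does the reference-only FDG-PET definition (11.4.2). This stands as evidence of intent. It does not supply a rule: Section 11.0 binds central review to the same criteria, so central review inherits the gap.

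The route to the primary endpoint is also narrow. A patient needs a baseline score of at least 11, a fall of more than 90% with 1 or 2 points left, no MIBG PD, and qualifying CT/MRI and marrow grades. That stands in full. The rounding argument stands in part: it would rescue 20 of the 30 pairs, including the example from baseline 20, but not the other 10.

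Three stronger readings are tempting and not supported:

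- A reader might infer that responders have been lost or the selection distorted. The documents give no baseline Curie distribution and do not report how reviewers graded such cases. The 30 pairs are combinations of scores, not patients.
- A reader might infer that a fall from 20 to 2 is itself a response. It is a PR on the MIBG parameter only; overall PR also depends on CT/MRI and marrow.
- A reader might infer that a patient left ungraded by the site escapes central review. Section 13.0 has every patient's day 43-50 MIBG scan submitted, and 11.3 uses the central Curie score. The score should be available; what is missing is the rule that turns it into a grade.

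**Conclusion.** Wrong as written. A relative score above 0 and below 0.1 has no MIBG grade, and no other section fills the gap. On unrounded scores this covers residual 1 with baseline 11 to 30 and residual 2 with baseline 21 to 30. Followed literally, the text denies responder status to a patient whose MIBG score fell by 90.5% to 96.7%, even where CT/MRI and marrow would permit overall PR.

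The intent is almost certainly PR, and the practical effect may be nil. The conclusion rests on a literal reading of the cut-offs and on unrounded scores; under the rounding assumed above, a third of the pairs (10 of 30) remain ungraded. It is worth correcting because the threshold feeds the primary endpoint directly and the correction is small.

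**What to change.** In 11.3(b), define PR as an unrounded relative score > 0 and ≤ 0.5 that does not meet 11.3(d) PD. Add no separate condition about new lesions: 11.3(d) already grades them as PD and exempts biopsy-negative ones, and a second condition would leave those exempted patients without a grade.

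Apply the rule to the centrally reviewed Curie scores of all patients, without knowledge of treatment arm. Then re-derive overall response under 11.6 with the CT/MRI and marrow grades, since regrading the MIBG parameter alone does not update the primary endpoint. Record the change as a dated clarification before the final analysis, and report by arm how many patients change MIBG grade and how many change overall response.

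The cost is one line of text and an arm-blind regrade from scans and grades the plan already collects. The small downside is an endpoint clarification made after the first interim analysis. Amendment 7A (Section 2.7.4) is a precedent: it clarified the marrow and overall-response criteria after that analysis.
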